#### **8.1.4.1. Reporting SAEs to Pfizer Safety**

All SAEs occurring in a subject during the active collection period are reported to Pfizer Safety on the CT SAE Report Form.

SAEs occurring in a subject after the active collection period has ended are reported to Pfizer Safety if the investigator becomes aware of them; at a minimum, all SAEs that the investigator believes have at least a reasonable possibility of being related to investigational product must be reported to Pfizer Safety.

Follow up by the investigator continues throughout and after the active collection period and until the event or its sequelae resolve or stabilize at a level acceptable to the investigator, and Pfizer concurs with that assessment.

If a subject begins a new anticancer therapy, SAEs occurring during the above-indicated active collection period must still be reported to Pfizer Safety irrespective of any intervening treatment.

#### **8.1.4.2. Recording Non-serious AEs and SAEs on the CRF**

During the active collection period, both non-serious AEs and SAEs are recorded on the CRF.

Follow-up by the investigator may be required until the event or its sequelae resolve or stabilize at a level acceptable to the investigator, and Pfizer concurs with that assessment.

If a subject begins a new anticancer therapy, the recording period for non-serious AEs ends at the time the new treatment is started; however, SAEs must continue to be recorded on the CRF during the above-indicated active collection period.

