**Table 13. Adverse Event Reporting**

Safety Event	Recorded on the CRF	Reported on the CT SAE Report Form to Pfizer Safety Within 24 Hours of Awareness
SAE	All	All
HSCT Day 0 until resume study therapy, death, withdrawal or post-treatment follow up: All deaths, Grade 3/Grade 4 treatment-related AEs, and treatment related SAEs	Related to glasdegib or placebo and deaths regardless of causality a	Serious and related to glasdegib or placebo and deaths regardless of causality
Non-serious AE	All	None
Exposure to the investigational product under study during pregnancy or breastfeeding, and occupational exposure	All (regardless of whether associated with an AE), except occupational exposure	Exposure during pregnancy, exposure via breastfeeding, occupational exposure (regardless of whether associated with an AE)
Note: Serious adverse events occurring to a patient after the active reporting period has ended should be reported to the sponsor if the investigator becomes aware of them; at a minimum, all serious adverse events that the investigator believes have at least a reasonable possibility of being related to study drug are to be reported to the sponsor. a. In Germany only: All SAEs, regardless of causality, will be recorded on the CRF.		

All observed or volunteered events regardless of treatment group or suspected causal relationship to the investigational product(s) will be reported as described in the following paragraphs.

Subjects must be followed for AEs for 28 days after the last treatment administration or until all drug-related toxicities have resolved, whichever is later; or earlier than 28 days should the patient commence another anticancer therapy in the meantime. For serious adverse events (SAEs), the active reporting period to Pfizer or its designated representative begins from the time that the patient provides informed consent, which is obtained prior to the patient's participation in the study, (ie, prior to undergoing any study related procedure and/or receiving investigational product), through and including 28 calendar days after the last administration of the investigational product. Serious adverse events occurring to a patient after the active reporting period has ended should be reported to the sponsor if the investigator becomes aware of them; at a minimum, all serious adverse events that the investigator believes have at least a reasonable possibility of being related to study drug are to be reported to the sponsor.

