### **8.1.4. Time Period for Collecting AE/SAE Information**

The time period for actively eliciting and collecting AEs and SAEs (“active collection period”) for each subject begins from the time the subject provides informed consent, which is obtained before the subject’s participation in the study (ie, before undergoing any study-related procedure and/or receiving investigational product), through and including a minimum of 28 calendar days after the last administration of the investigational product.

For subjects who are screen failures, the active collection period ends when screen failure status is determined.

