### 3.5. Safety Endpoints

Safety endpoints will be summarized based on the on-treatment period unless otherwise specified.

On-treatment is defined as the time from the first dose of study treatment to last dose prior to HSCT + 28 days and if applicable, from first dose post-HSCT to last dose + 28 days or start of new anti-cancer drug therapy (minus 1 day), whichever occurs first. Note that conditioning regimens for HSCT (regardless of whether glasdegib is resumed after HSCT) are not considered “new anti-cancer drug therapy”. Adverse events occurring on the same day as the first dose of study treatment will be considered to have occurred during the on-treatment period. All other assessments which occur on the same day as the first dose of study treatment will be considered baseline assessments (see [Section 3.4](#) for the definition of baseline).

Safety data collected outside the on-treatment period as described above will be listed but not summarized.

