### 6.6.2. Deaths

The frequency (number and percentage) of patients in the safety analysis set who died during the study and who died within 28 days after last dose of study treatment as well as the primary reason for death, will be tabulated based on information from the ‘Notice of Death’ CRF, by treatment arm.

The frequency (number and percentage) of patients in the safety analysis set who died within 30 days of first dose of study treatment will also be provided.

Date and cause of death will be provided in individual patient data listing together with selected dosing information (study treatment received, date of first/last administration, dose).

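### SAEs with onset after new anti-cancer drug therapy but within 28 days of the last dose are collected on the CRF, yet fall outside the treatment-emergent SAE, Grade 5 and disclosure SAE tables

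*Protocol*

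**What the plan says.** **Collection (protocol).** Section 8.1.4 runs active collection from consent "through and including a minimum of 28 calendar days after the last administration of the investigational product". Section 8.1.4.2 then separates two streams once new anticancer therapy begins. Recording of non-serious AEs stops, but "SAEs must continue to be recorded on the CRF during the above-indicated active collection period". Section 8.1.4.1 has the matching rule for expedited reporting: "SAEs occurring during the above-indicated active collection period must still be reported to Pfizer Safety irrespective of any intervening treatment". There is one stated limit. From HSCT Day 0 until study drug resumes, Table 13 restricts CRF recording to events "Related to glasdegib or placebo and deaths regardless of causality", with all SAEs recorded in Germany.

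**Summary (SAP).** Section 3.5 defines on-treatment in two segments. The first runs from first dose to 28 days after the last dose before HSCT. The second, if applicable, runs "from first dose post-HSCT to last dose + 28 days or start of new anti-cancer drug therapy (minus 1 day), whichever occurs first". Conditioning for HSCT does not count as new drug therapy. The section closes: "Safety data collected outside the on-treatment period as described above will be listed but not summarized". Section 3.5.1 makes an AE treatment emergent if it occurs in the on-treatment period, and section 6.6.1 builds its AE tables on treatment-emergent events unless it states otherwise.

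**Deaths (SAP).** Section 6.6.2 tabulates patients "who died during the study and who died within 28 days after last dose of study treatment", with the primary reason for death. It has no cut at new therapy.

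**The concern.** The protocol keeps collecting SAEs after new therapy where it lets non-serious AEs go. The SAP applies one cut to both, so data that the protocol asks sites to record do not reach the tables that compare the arms.

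Two things are at stake. First, new drug therapy is a post-randomization event, and it is plausibly linked to treatment failure: Protocol 5.5.1.2 requires patients with residual or resistant leukemia after the second induction to stop treatment. A window that closes at that point can differ in length between arms if failure rates differ. Second, the treatment-emergent Grade 5 table need not reconcile with the 28-day deaths table, and the report would have to explain each gap patient by patient.

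The cut also does not depend on causality. An SAE that the investigator attributes to glasdegib or placebo is left out of the treatment-related SAE table if it begins after new drug therapy. The same applies to mQTcF prolongation above Grade 2, which Protocol 8.4.1 makes reportable as an SAE for 28 days after the last dose whatever its cause.

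**Working it through.** The plan states no figure to reproduce here. The check compares the two windows and then does some simple arithmetic.

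**1. One patient traced through both documents.** Take the last dose as day 0, new drug therapy on day 10, sepsis with onset on day 20 and death on day 25.

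- Protocol 8.1.4.2: onset on day 20 is within 28 days, so the event is recorded as an SAE.
- SAP 3.5: the window closes on day 10 - 1 = 9, so the event is listed but not summarized.
- SAP 3.5.1 and 6.6.1: it is not treatment emergent, so it is absent from the SAE and Grade 5 tables, and from the treatment-emergent SAE table for US and EU disclosure in 6.6.1.1.
- SAP 6.6.2: death on day 25 is within 28 days, so it is counted.

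If the sepsis had begun on day 8, it would be treatment emergent and would stay in the tables even though death came later. The gap depends on onset date.

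**2. Days lost.** If new drug therapy starts on day d (1 to 28), the window ends on day d - 1. Days d to 28 are lost, which is 28 - d + 1 = 29 - d days.

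| d | Days lost | Share of 28 days |
|---|---|---|
| 1 | 28 | 100% |
| 7 | 22 | 79% |
| 14 | 15 | 54% |
| 21 | 8 | 29% |
| 28 | 1 | 4% |
| 29 or later | 0 | 0% |

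**3. Patients affected (assumptions only).** Let f be the share of an arm starting new drug therapy within 28 days of the last dose, and q the 28-day risk of an SAE onset, with constant hazard. The documents give no value for f, d or q. Arm sizes are 400/2 = 200 (intensive) and 320/2 = 160 (non-intensive).

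Patients with an SAE onset in the lost days = n x f x [1 - (1 - q)^((29 - d)/28)].

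- Low end (f = 5%, d = 21, q = 10%): 200 x 0.05 x [1 - 0.9^(8/28)] = 0.3; with n = 160, 0.2.
- Middle (f = 15%, d = 14, q = 30%): 200 x 0.15 x [1 - 0.7^(15/28)] = 5.2; with n = 160, 4.2.
- High end (f = 30%, d = 7, q = 50%): 200 x 0.30 x [1 - 0.5^(22/28)] = 25.2; with n = 160, 20.2.

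The range runs from about 0.3 to 25 patients per 200, too wide to serve as an estimate. Some of these patients would already be counted for an earlier SAE, so the number with any SAE would change by less.

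**4. What the visible SAP does summarize outside the window.** Deaths (6.6.2) have no cut at new therapy. Section 6.6.1 plans tables of non-treatment-emergent events during HSCT. In 6.6.1.1 the fatal-AE item lacks the treatment-emergent label that the two items before it carry, so its window is not stated.

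**The case against.** The strongest reply is that a collection window and a summary window need not match. Protocol section 9 lets the SAP modify the outlined analyses. Protocol 9.5.1 puts the emphasis on treatment-emergent events and sets no summary window for SAEs. SAP version 4 updated the on-treatment definition, so the window was revisited. Ending it at new drug therapy keeps the toxicity of the next regimen out of a study-drug table, and the later events are still listed and still reported to the sponsor's safety group. This stands as a reason to keep the treatment-emergent tables. It does not answer the need for an arm comparison of the later SAEs, which a listing cannot give.

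Three stronger readings are tempting, and the documents do not support them.

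- **That no summary table contains these events.** Deaths and HSCT-period events are tabulated, and the scope of the fatal-AE table is open. The text after the first treatment-emergent criterion in SAP 3.5.1 and a block after SAP 6.6.1.1 are redacted, so a claim about every table cannot be made.
- **That the SAE comparison is biased towards glasdegib.** No difference in failure rates is given. If placebo has more early failures, the cut removes more placebo time. A window without the cut also depends on outcome, because the arm with more failures takes in more events from the next regimen.
- **That a specific number of patients is lost, mostly early failures.** A reader might start from the 55% CR/CRi rate in the earlier single-arm cohort and multiply by guessed shares. Every factor after the first would be a guess. Protocol 8.2.3 also excludes hospitalization for signs and symptoms of progression from SAE reporting, which lowers the SAE risk in this group.

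The wording of SAP 3.5 is also ambiguous. The cut sits in the post-HSCT clause and can be read as applying to that segment only. On that reading, patients who fail induction would not be cut at all. This limits the point, but it is also a reason to clarify the text.

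**Conclusion.** The point holds in a narrow form. If the new-therapy cut in SAP 3.5 applies to both segments, SAEs and Grade 5 events with onset after new drug therapy but within 28 days of the last dose are on the CRF and in listings, but outside the treatment-emergent SAE, Grade 5 and disclosure SAE tables. If the cut applies to the post-HSCT segment only, the gap is confined to patients who resumed study drug after HSCT.

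The loss per affected patient is exact: 29 - d days. The number of events lost, which patients they come from and any direction of bias cannot be computed from the documents. The counts are low only relative to the protocol's recording window. The mismatch with the deaths table is a reconciliation problem and not an error in either table. This is an inexpensive improvement to the safety reporting; the treatment-emergent tables are not invalid.

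**What to change.** - **SAP 6.6.1 and 6.6.1.1:** keep the current treatment-emergent tables. Add a by-arm summary of SAEs and Grade 5 events from first dose to last dose + 28 days regardless of new therapy, with onset after new therapy on a separate line. Footnote that collection between HSCT Day 0 and resumption of study drug is limited.
- **SAP 6.6.1.1:** state the time window of the fatal-AE table.
- **SAP 3.5:** say whether the new-therapy cut applies to both the pre- and post-HSCT segments, and what the window is for a patient without HSCT.

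**Cost:** SAP wording, one derived flag and one added summary. The protocol already requires the data on the CRF. The downside is that some of the added events will be due to the new therapy; the separate line makes that visible. The truncation stays right for non-serious AEs, whose recording stops at that point.

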### **8.1.5. Causality Assessment**

The investigator's assessment of causality must be provided for all AEs (serious and non-serious); the investigator must record the causal relationship on the CRF, and report such an assessment in accordance with the SAE reporting requirements, if applicable. An investigator's causality assessment is the determination of whether there exists a reasonable possibility that the investigational product caused or contributed to an AE; generally the facts (evidence) or arguments to suggest a causal relationship should be provided. If the investigator does not know whether or not the investigational product caused the event, then the event will be handled as "related to investigational product" for reporting purposes, as defined by the sponsor. If the investigator's causality assessment is "unknown but not related" to investigational product, this should be clearly documented on study records.

In addition, if the investigator determines that an SAE is associated with study procedures, the investigator must record this causal relationship in the source documents and CRF, and report such an assessment in the dedicated section of the CT SAE Report Form and in accordance with the SAE reporting requirements.

### **8.1.6. Sponsor's Reporting Requirements to Regulatory Authorities**

AE reporting, including suspected unexpected serious adverse reactions, will be carried out in accordance with applicable local regulations.

## **8.2. Definitions**

### **8.2.1. Adverse Events**

An AE is any untoward medical occurrence in a study subject administered a product or medical device; the event need not necessarily have a causal relationship with the treatment or usage. Examples of AEs include, but are not limited to:

- Abnormal test findings;
- Clinically significant signs and symptoms;
- Changes in physical examination findings;
- Hypersensitivity;
- Drug abuse;
- Drug dependency.

Additionally, AEs may include signs and symptoms resulting from:

- Drug overdose;
- Drug withdrawal;
- Drug misuse;
- Drug interactions;
- Extravasation;
- Exposure during pregnancy (EDP);
- Exposure via breastfeeding;
- Medication error;
- Occupational exposure.

Worsening of signs and symptoms of the malignancy under study should be recorded as AEs in the appropriate section of the CRF. Disease progression assessed by measurement of malignant lesions on radiographs or other methods should not be reported as AEs.

### **8.2.2. Abnormal Test Findings**

Abnormal objective test findings should be recorded as AEs when any of the following conditions are met:

- Test result is associated with accompanying symptoms; and/or
- Test result requires additional diagnostic testing or medical/surgical intervention; and/or
- Test result leads to a change in study dosing (outside of any protocol-specified dose adjustments) or discontinuation from the study, significant additional concomitant drug treatment, or other therapy; and/or
- Test result is considered to be an AE by the investigator or sponsor.

Merely repeating an abnormal test, in the absence of any of the above conditions, does not constitute an AE. Any abnormal test result that is determined to be an error does not require recording as an AE.

### 8.2.3. Serious Adverse Events

A serious adverse event is any untoward medical occurrence at any dose that:

- Results in death;
- Is life-threatening (immediate risk of death);
- Requires inpatient hospitalization or prolongation of existing hospitalization;
- Results in persistent or significant disability/incapacity (substantial disruption of the ability to conduct normal life functions);
- Results in congenital anomaly/birth defect.

Or that is considered to be:

- An important medical event.

Medical and scientific judgment is exercised in determining whether an event is an important medical event. An important medical event may not be immediately life-threatening and/or result in death or hospitalization. However, if it is determined that the event may jeopardize the subject or may require intervention to prevent one of the other AE outcomes, the important medical event should be reported as serious.

Examples of such events are intensive treatment in an emergency room or at home for allergic bronchospasm; blood dyscrasias or convulsions that do not result in hospitalization; or development of drug dependency or drug abuse.

Progression of the malignancy under study (including signs and symptoms of progression) should not be reported as an SAE unless the outcome is fatal within the active collection period. Hospitalization due to signs and symptoms of disease progression should not be reported as an SAE. If the malignancy has a fatal outcome during the study or within the active collection period, then the event leading to death must be recorded as an AE on the CRF, and as an SAE with Common Terminology Criteria for Adverse Events (CTCAE) Grade 5 (see the [Severity Assessment](#) section).

CCI

CCI

### 8.3. Severity Assessment

AEs will be reported using concise medical terminology (verbatim) as well as the Common Terminology Criteria (CTC) term for Adverse Events (Version 4.03, Publish Date: June 14, 2010, <http://ctep.cancer.gov/reporting/ctc.html>) listed in the Cancer Therapy Evaluation Program.

The investigator may use the following definitions of Severity in accordance with CTCAE Version 4.03 to describe the maximum intensity of the adverse event:

GRADE	Clinical Description of Severity
0	No change from normal or reference range (This grade is not included in the Version 4.03 CTCAE document but may be used in certain circumstances.)
1	MILD adverse event
2	MODERATE adverse event
3	SEVERE adverse event
4	LIFE-THREATENING consequences; urgent intervention indicated
5	DEATH RELATED TO adverse event

Note the distinction between the severity and the seriousness of an AE. A severe event is not necessarily an SAE. For example, a headache may be severe (interferes significantly with the subject's usual function) but would not be classified as serious unless it met one of the criteria for SAEs, listed above.

### 8.4. Special Situations

#### 8.4.1. Protocol-Specified Serious Adverse Events

All cases of Grade >2 mQTcF prolongation regardless of causality and treatment arm must be reported as an SAE for up to 28 calendar days after the last dose of study drug administered. All SAEs will be reported to Pfizer Safety by the investigator as described in previous sections, and will be handled as SAEs in the safety database.

#### 8.4.2. Potential Cases of Drug-Induced Liver Injury

Humans exposed to a drug who show no sign of liver injury (as determined by elevations in transaminases) are termed "tolerators," while those who show transient liver injury, but adapt are termed "adaptors." In some subjects, transaminase elevations are a harbinger of a more serious potential outcome. These subjects fail to adapt and therefore are "susceptible" to progressive and serious liver injury, commonly referred to as drug-induced liver injury (DILI). Subjects who experience a transaminase elevation above 3 times the upper limit of normal ( $\times$  ULN) should be monitored more frequently to determine if they are an "adaptor" or are "susceptible."

In the majority of DILI cases, elevations in aspartate aminotransferase (AST) and/or alanine aminotransferase (ALT) precede total bilirubin (TBili) elevations ( $>2 \times \text{ULN}$ ) by several days or weeks. The increase in TBili typically occurs while AST/ALT is/are still elevated above  $3 \times \text{ULN}$  (ie, AST/ALT and TBili values will be elevated within the same lab sample). In rare instances, by the time TBili elevations are detected, AST/ALT values might have decreased. This occurrence is still regarded as a potential DILI. Therefore, abnormal elevations in either AST OR ALT in addition to TBili that meet the criteria outlined below are considered potential DILI (assessed per Hy's law criteria) cases and should always be considered important medical events, even before all other possible causes of liver injury have been excluded.

The threshold of laboratory abnormalities for a potential DILI case depends on the subject's individual baseline values and underlying conditions. Subjects who present with the following laboratory abnormalities should be evaluated further as potential DILI (Hy's law) cases to definitively determine the etiology of the abnormal laboratory values:

- Subjects with AST/ALT and TBili baseline values within the normal range who subsequently present with AST OR ALT values  $>3 \times \text{ULN}$  AND a TBili value  $>2 \times \text{ULN}$  with no evidence of hemolysis and an alkaline phosphatase value  $<2 \times \text{ULN}$  or not available;
- For subjects with baseline AST **OR** ALT **OR** TBili values above the ULN, the following threshold values are used in the definition mentioned above, as needed, depending on which values are above the ULN at baseline:
  - Preexisting AST or ALT baseline values above the normal range: AST or ALT values  $>2$  times the baseline values AND  $>3 \times \text{ULN}$ ; or  $>8 \times \text{ULN}$  (whichever is smaller);
  - Preexisting values of TBili above the normal range: TBili level increased from baseline value by an amount of at least  $1 \times \text{ULN}$  **or** if the value reaches  $>3 \times \text{ULN}$  (whichever is smaller).

Rises in AST/ALT and TBili separated by more than a few weeks should be assessed individually based on clinical judgment; any case where uncertainty remains as to whether it represents a potential Hy's law case should be reviewed with the sponsor.

The subject should return to the investigator site and be evaluated as soon as possible, preferably within 48 hours from awareness of the abnormal results. This evaluation should include laboratory tests, detailed history, and physical assessment. The possibility of hepatic neoplasia (primary or secondary) should be considered.

In addition to repeating measurements of AST and ALT and TBili, laboratory tests should include albumin, creatine kinase (CK), direct and indirect bilirubin, gamma-glutamyl transferase (GGT), prothrombin time (PT)/international normalized ratio (INR), total bile acids, alkaline phosphatase and acetaminophen drug and/or protein adduct levels. Consideration should also be given to drawing a separate tube of clotted blood and an

anticoagulated tube of blood for further testing, as needed, for further contemporaneous analyses at the time of the recognized initial abnormalities to determine etiology. A detailed history, including relevant information, such as review of ethanol, acetaminophen (either by itself or as a coformulated product in prescription or over-the-counter medications), recreational drug, supplement (herbal) use and consumption, family history, sexual history, travel history, history of contact with a jaundiced person, surgery, blood transfusion, history of liver or allergic disease, and potential occupational exposure to chemicals, should be collected. Further testing for acute hepatitis A, B, C, D, and E infection and liver imaging (eg, biliary tract) may be warranted.

All cases demonstrated on repeat testing as meeting the laboratory criteria of AST/ALT and TBili elevation defined above should be considered potential DILI (Hy's law) cases if no other reason for the LFT abnormalities has yet been found. **Such potential DILI (Hy's law) cases are to be reported as SAEs, irrespective of availability of all the results of the investigations performed to determine etiology of the LFT abnormalities.**

A potential DILI (Hy's law) case becomes a confirmed case only after all results of reasonable investigations have been received and have excluded an alternative etiology.

